7.3.1.2. Laboratory test

Recommended laboratory tests and time points are included in Table 4. Test results of chest X-ray, erythrocyte sedimentation rate (ESR), C-reactive protein (CRP), other blood chemistry, hematology, and tuberculin test should be recorded, if conducted.

Table 4 Recommended Laboratory Test

	Lymphocyte	Neutrophils	Hemoglobin	Lipids (TC, HDL, LDL)
Baseline	X	X	X	X
4 to 8 weeks after treatment		X	X	X
Every 3 months	X	X	X	

Abbreviations: TC=total cholesterol, HDL= high density lipoprotein, LDL=low density lipoprotein.

In case there are any clinically significant laboratory abnormalities (as per the investigator's judgment) that occur after the treatment of Xeljanz compared to baseline, the tests should be recorded in detail on the CRF, including test results before and after Xeljanz treatment, a causal relationship to Xeljanz, and any comments from the investigator.

Please refer to [Section 9.4.1](#) for the criteria for determining whether an abnormal objective test finding should be reported as an AE.

7.3.2. Effectiveness variables

The Mayo score or the Partial Mayo score at week 8, 16, 24 and also 52 for the long-term users is assessed to see the remission, clinical response or mucosal healing. Investigator will perform the final effectiveness evaluation of the drug into 4 categories based on the clinical impression plus Mayo score or Partial Mayo score ('Improved', 'Unchanged', 'Aggravated', 'Not assessable').

7.3.3. Effectiveness evaluation

Effectiveness assessment will be performed by the accredited investigator in the Korean health care center. The investigator will perform the final effectiveness evaluation at baseline and after 8, 16 and 24 weeks of treatment based on the clinical impression and any of the commonly used effectiveness assessment criteria such as Mayo score or Partial Mayo score, and record the assessment results in each patient's CRF. 52nd week will be added for the long-term users. If the patient does not complete the 24 or 52 weeks of treatment, relevant data should be collected based on the last assessment performed at the time of treatment discontinuation. The final evaluation of the effectiveness will be determined by the investigator into 4 categories('Improved', 'Unchanged', 'Aggravated', 'Not assessable').

- Improved (Symptoms of ulcerative colitis have improved or showed adequate maintenance effect after taking Xeljanz)
- Unchanged (Symptoms have not changed much since taking Xeljanz)
- Aggravated (Symptoms have worsened after taking Xeljanz)
- Not assessible (Reason :)

If the overall effectiveness assessment is evaluated as 'Improved', 'Unchanged' or 'Aggravated', it is analyzed to be clinically significant. If the overall effectiveness assessment is evaluated as 'Not assessible', it is analyzed as not clinically significant. Among the 4 categories, 'Improved' is considered that the drug is effective. 'Unchanged' and 'Aggravate' are considered that there is a lack of effectiveness.

The Mayo score or the Partial Mayo score, which is referred in the effectiveness evaluation, are commonly used in actual medical practice. The Mayo score or the Partial Mayo Score at 8, 16 and 24 weeks(also 52 for the long-term users) will be assessed after the administration of Xeljanz, and Mayo Score measures the number of stool frequency, rectal bleeding, findings of endoscopy, and physician's global assessment. In total, based on the total score of 12 points, 0-2 points is rated as Remission, 3-5 as Mild, 6-10 as Moderate, and 11-12 as Severe. Partial Mayo Score is calculated by the sum of the remaining evaluations, except for the findings of endoscopy score. Based on the total score of 9 points, 0-1 is rated as Remission, 2-4 as Mild, 5-6 as Moderate and 7-9 as Severe.

Remission is defined as Mayo score being less than or equal to 2 (in case of partial Mayo score, the score is less than or equal to 1) and other subscores not greater than 1 and rectal bleeding score of 0. Clinical response is defined as a decrease of Mayo score of more than 3 points and 30% from the baseline and a decrease of 1 or more in rectal bleeding score or rectal bleeding score of 0 or 1. Clinical response per partial Mayo score is a decrease of partial Mayo score of 2 or more and 30 % from the baseline and a decrease of 1 or more in rectal bleeding score or rectal bleeding score of 0 or 1. Clinical remission is defined as Mayo score being less than or equal to 2 and other subscores not bigger than 1. Endoscopic remission is endoscopic subscore of 0 and mucosal healing is defined as an endoscopic score of 0 or 1.

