7. RESEARCH METHODS

7.1. Study design

This is an open-label, non-comparative, non-interventional, prospective, and multi-center study conducted in Korean health care centers by accredited physicians (ie, investigators). The study population will be adult patients with moderately to severely active UC who have had an inadequate response or intolerance to the basic treatments or biological agents. Clinical Severity of Ulcerative Colitis is classified as mild, moderate, or severe based on the Mayo score of Partial Mayo score. (Table 1).

Table 1. Mayo Score for ulcerative colitis⁴

Variables/Score		Criteria
Stool frequency	0	Normal number of stool
	1	1-2 stools more than normal
	2	3-4 stools more than normal
	3	≥5 stools more than normal
Rectal bleeding	0	No blood seen
	1	Streaks of blood with stool less than half the time
	2	Obvious blood with stool most of the time
	3	Blood alone passed
Findings of proctosigmoidoscopy	0	Normal or inactive disease
	1	Mild disease (erythema, decreased vascular pattern, mild friability)
	2	Moderate disease (marked erythema, absent vascular pattern, friability, erosions)
	3	Severe disease (spontaneous bleeding, ulceration)
Physician's global assessment	0	Normal
	1	Mild
	2	Moderate
	3	Severe

Xeljanz will be administered according to the “Dosage and Administration” of the approved labeling. There is no visit or activity mandated by this study. The investigator will collect patient data and record the information on each patient’s case report form (CRF).

Each investigator will sequentially enroll all patients to whom Xeljanz is prescribed for the first time according to the local product label, and who agree to participate in this study by signing the data privacy statement. Safety is the primary endpoint of this study, which will be assessed based on adverse events (AEs) that have occurred between the first dose of Xeljanz to the next visit.

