As a secondary endpoint, the investigator will perform the final effectiveness evaluation based on the clinical impression plus the Mayo score or Partial Mayo score. The Mayo score or the Partial Mayo Score at week 8, 16 and 24(also 52 for the long-term users) is assessed to see the remission, clinical response or mucosal healing. To assess the effectiveness of the Xeljanz. Mayo score is based on a total score of 12 points by evaluating and calculating the four clinical evaluation criteria: Stool frequency, Rectal bleeding, Findings of endoscopy, and Physician's global assessment. (Table 1) Partial Mayo Score is calculated by the sum of the remaining evaluations, except for the findings of endoscopy score.

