## **Statistical Analysis Plan for rPMS**

- Achieved
- Not achieved

3) Remission

Remission is defined as Mayo score being less than or equal to 2 (in case of partial Mayo score, the score is less than or equal to 1) and other subscores not greater than 1 and rectal bleeding score of 0.

- Achieved
- Not achieved

4) Clinical response

Clinical response is defined as a decrease of Mayo score of more than 3 points and 30% from the baseline and a decrease of 1 or more in rectal bleeding score or rectal bleeding score of 0 or 1. Clinical response per partial Mayo score is a decrease of partial Mayo score of 2 or more 30% from the baseline and decrease of 1 or more in rectal bleeding score or rectal bleeding score of 0 or 1.

- Achieved
- Not achieved

5) The final efficacy evaluation determined by the investigator

- Effective
  - Improved
- Not-effective
  - Unchanged
  - Aggravated

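### The full-Mayo clinical response rule (a fall of more than 3 points and 30%) has a 30% condition that can never act; confirm the intended threshold and align Protocol 7.3.3 with SAP 4.2

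*Protocol*

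**What the plan says.** Protocol 7.3.3 sets the full-Mayo rule as "a decrease of Mayo score of more than 3 points and 30% from the baseline", together with a bleeding condition: "a decrease of 1 or more in rectal bleeding score or rectal bleeding score of 0 or 1". SAP 4.2 item 4 repeats the threshold: "Clinical response is defined as a decrease of Mayo score of more than 3 points and 30% from the baseline".

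The next sentence of Protocol 7.3.3 gives the partial-Mayo rule in inclusive form: "a decrease of partial Mayo score of 2 or more and 30 % from the baseline", with the same bleeding condition. The SAP version loses the conjunction between points and percentage: "a decrease of partial Mayo score of 2 or more 30% from the baseline".

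On the scale itself, Protocol 7.1 states that "Mayo score is based on a total score of 12 points by evaluating and calculating the four clinical evaluation criteria", and Table 1 scores each of the four items 0, 1, 2 or 3. Protocol 7.3.3 gives the bands: "based on the total score of 12 points, 0-2 points is rated as Remission, 3-5 as Mild, 6-10 as Moderate, and 11-12 as Severe". On the population, Protocol 7.1 states: "The study population will be adult patients with moderately to severely active UC". By those bands, that is a full Mayo score of 6 to 12 at baseline.

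SAP 6.3 item 4 tabulates clinical response as achieved or not achieved at weeks 8, 16 and 24. SAP 6.4 adds week 52 for long-term users.

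**The concern.** A rule with two joined conditions should have cases in which each one decides the result. Here the percentage condition looks idle, because any whole-number fall that passes the points condition already passes it. The partial-Mayo rule beside it has the same structure but an inclusive points threshold, and its percentage condition does work. That contrast suggests a slip in the full-Mayo wording.

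What is at stake is the tabulated response rate among patients with full Mayo scores. If an inclusive threshold was meant, exact 3-point falls from the moderate band that meet the bleeding condition are being reported as non-response. The plan also accepts either score without saying which rule governs when both can be computed, so one patient could be a responder on one scale and not on the other.

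**Working it through.** The documents state no figure for this point, so there is nothing to reproduce. The check is an enumeration over whole-number scores.

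**Inputs.** Four items scored 0–3 (Table 1), so the total runs from 0 to 12 and every fall is a whole number. Moderate is 6–10 and severe 11–12 (Protocol 7.3.3). The partial score omits endoscopy and runs from 0 to 9.

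**Step 1: the rule as written.** More than 3 points means a fall d ≥ 4. At baseline b the percentage fall is 100 × d/b. Its smallest value is at d = 4, b = 12: 100 × 4/12 = 33.3%. No combination of baseline up to 12 and fall of 4 or more fails the percentage condition, whether it is read as ≥30% or >30%. The condition is redundant at every baseline.

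**Step 2: full Mayo with 3 points or more, for comparison.**

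| Baseline | 3-point fall, % of baseline | 4-point fall, % of baseline | Smallest qualifying fall as written | Smallest qualifying fall if ≥3 and ≥30% |
|---|---|---|---|---|
| 6 | 50.0 | 66.7 | 4 | 3 |
| 7 | 42.9 | 57.1 | 4 | 3 |
| 8 | 37.5 | 50.0 | 4 | 3 |
| 9 | 33.3 | 44.4 | 4 | 3 |
| 10 | 30.0 | 40.0 | 4 | 3 (4 if strictly >30%) |
| 11 | 27.3 | 36.4 | 4 | 4 |
| 12 | 25.0 | 33.3 | 4 | 4 |

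Under the inclusive reading the 30% condition acts at baselines 11 and 12, and also at 10 if 30% is strict. The two readings differ only for exact 3-point falls from baselines 6–10 (6–9 if strict).

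**Step 3: the partial-Mayo rule.** With a fall of 2 or more, a 2-point fall is 2/7 = 28.6%, 2/8 = 25.0% and 2/9 = 22.2% of baselines 7, 8 and 9. It fails 30% at each, so the condition raises the required fall to 3 there.

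**Step 4: the bottom of the moderate band.** From baseline 6, a 4-point fall lands on 6 − 4 = 2, which is inside the plan's remission band of 0–2. The patient must reach the remission score to count as a response, although the SAP reports the two outcomes separately. (Remission also carries subscore conditions, so the two are not identical.) On the partial rule, baseline 5 responds at 5 − 2 = 3, a fall of 40%, which is in the mild band.

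**Step 5: the two scales can disagree.** Take a full Mayo of 9 (partial 6, endoscopy 3) falling to 6 (partial 4, endoscopy 2), with the bleeding condition met. The full fall is 3, so non-response as written. The partial fall is 2, or 2/6 = 33.3%, so response.

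Enumerating all subscore profiles with an exact 3-point full-Mayo fall from baseline 6–10 that meet the bleeding condition gives 3,342 profiles. Of these, 2,289 (68%) already meet the partial rule. If no item is allowed to worsen, the figures are 844 of 1,095 (77%). Profiles are weighted equally, so these shares are illustrative and not patient estimates.

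**Step 6: a ceiling on size, by assumption.** The documents give no distribution of falls. Assume a normal distribution rounded to whole numbers: P(fall = 3) = Φ((3.5 − μ)/σ) − Φ((2.5 − μ)/σ).

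| Mean μ | P(fall = 3) for σ from 2.5 to 3.5 |
|---|---|
| 3 | 11.4–15.9% |
| 4 | 10.9–14.7% |
| 5 | 9.7–11.6% |
| 6 | 7.8–8.1% |

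This is a share of patients with full Mayo at both baseline and visit. Baselines 11–12 and failures of the bleeding condition have still to be subtracted.

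**The case against.** The strongest reply is that redundancy is not contradiction. The full-Mayo rule can be computed and reads the same in both documents, and an idle clause misclassifies nobody relative to the rule as stated. That stands.

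A reader might go further and infer that the 30% clause has a function only if the points clause reads 3 or more, so that 3 or more must be the intended rule. The documents do not support this. The clause would also act with 2 or more (baselines 7–12), with 1 or more (6–12), or with the present points threshold and a percentage above 33.3%. The arithmetic shows that something in the rule is idle, but not which element is wrong. The inclusive partial rule and the baseline-6 result make 3 or more the likeliest reading and no more than that.

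A reader might also take 8–16% as the share of patients who would change from non-response to response. That is unsupported too. It is an assumed ceiling among fully scored patients. Full Mayo needs endoscopy at both times, the SAP treats endoscopy as conditional, and no visit is mandated. Many affected profiles already meet the partial rule, and the plan states no precedence.

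Finally, the consequence is limited. Safety is the primary endpoint. Clinical response is reported only as frequency and percentage. The subgroup tests and logistic regression in SAP 6.3 use the investigator's final assessment, which does not apply this threshold. This stands and sets the severity.

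**Conclusion.** The point holds as a minor defect of definition. The 30% condition in the full-Mayo rule never acts, and this follows from the plan's own scale without any outside definition. That an inclusive threshold was intended is likely but not proved.

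If it was intended, the patients affected are those with endoscopy at baseline and at the visit, a baseline of 6–10 (6–9 if 30% is strict), an exact 3-point fall, and the bleeding condition met. From baselines 11–12 a 3-point fall is non-response under either reading. The net change in the response rate cannot be estimated from the documents. The ceiling of about 8–16% of fully scored patients rests wholly on the assumed normal falls with mean 3–6 and SD 2.5–3.5. The primary safety results and the investigator's effectiveness category are untouched.

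**What to change.** Before analysis, the sponsor should confirm the intended full-Mayo threshold and align Protocol 7.3.3 and SAP 4.2 item 4.

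- Unless the strict threshold is confirmed, write the full-Mayo condition in both documents as *a decrease of 3 points or more and of 30% or more*. This also settles that 30% is inclusive, which decides baseline 10.
- If the strict threshold is confirmed, delete the idle 30% clause and tabulate the version with 3 or more and 30% or more as a sensitivity analysis.
- In either case, restore the conjunction in the SAP's partial-Mayo rule: *2 points or more and 30% or more*.

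The cost is one line in each document and one programming condition. No new data are needed.

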7.4. Data sources

7.4.1. Case report forms

The investigator will review source documents and complete an electronic CRF for each included patient. The completed original CRFs are the sole property of Pfizer and should not be made available in any form to the third parties, except for authorized representatives of Pfizer or appropriate regulatory authorities, without written permission from Pfizer.

The investigator has ultimate responsibility for the collection and reporting of all clinical, safety, and laboratory data entered on the CRFs, and ensuring that they are accurate, authentic/original, attributable, complete, consistent, legible, timely (contemporaneous), enduring, and available when required. The CRFs must be signed by the investigator or by an authorized staff member to attest that the data contained on the CRFs is true. Any corrections to entries made on the CRFs must be dated, initialed and explained (if necessary) and should not obscure the original entry.

In most cases, the source documents are the hospital's or the physician's patient chart. In these cases data collected on the CRFs must match the data in those charts.

7.4.2. Record retention

To enable evaluations and/or audits from regulatory authorities or Pfizer, the investigator agrees to keep records, including the identity of all participating patients (sufficient information to link records, eg, CRFs and hospital records), copies of all CRFs, SAE forms, source documents, and detailed records of treatment disposition, and adequate documentation of relevant correspondence (eg, letters, meeting minutes, telephone calls reports). The records should be retained by the investigator according to local regulations, or as specified in the Clinical Study Agreement, whichever is longer.

If the investigator becomes unable for any reason to continue to retain study records for the required period (eg, retirement, relocation), Pfizer should be prospectively notified. The study records must be transferred to a designee acceptable to Pfizer, such as another investigator, another institution, or to an independent third party arranged by Pfizer. Investigator records must be kept for a minimum of 15 years after completion or discontinuation of the study or as required by applicable local regulations. The investigator must obtain Pfizer's written permission before disposing of any records, even if retention requirements have been met.

CCI

7.6. Data management

CRF data collected by the investigator will be entered into the clinical database. Verifications will be performed after comparison of the double data entry. All missing data or data to be checked will be reported on a query sheet for further verification at the study site. Any data modification will be recorded.

AEs and Medical history will be coded using the MedDRA(Medical Dictionary for Regulatory Activities). Concomitant medication will be coded via ATC code.

Statistical analysis will be carried out with SAS software version 9.2 or a more recent version.

7.7. Data analysis

Analysis will be performed for the pooled data collected by each investigator during the re-examination period. Total number of centers participating, total number of cases enrolled and retrieved, and total number of cases included in the analysis will be presented in summary tables. Evaluation of data will primarily consist of summary displays (eg, descriptive statistics, tables, and graphs).

Detailed methodology for summary and statistical analyses of data collected in this study will be documented in a Statistical Analysis Plan (SAP), which will be dated, filed and maintained by Pfizer. The SAP may modify the plans outlined in the protocol; any major modifications of primary endpoint definitions or their analyses will be reflected in a protocol amendment.

7.7.1. Safety analysis

The primary interest of this study is the incidence of AEs investigated during the re-examination period. Incidence of each AE will be presented with 95% confidence interval. Serious, related, and/or unexpected AEs will be summarized separately.

[figure not shown]
Safety analysis will be performed for all patients registered for this study who are prescribed at least 1 dose of Xeljanz according to the local label and followed up for safety data.

To identify the factors that affect safety, subgroup analysis for various factors will be performed, including the classification of AEs by body system, and comparison of incidence of AEs by sex, age, presence of concurrent diseases, presence of concomitant medications, baseline disease activity, etc.

In case the drug was administered to special populations such as elderly people over 65, or patients with renal or hepatic disorders during the study, subgroup analysis will also be performed for each of those populations. The safety and effectiveness of Xeljanz in pediatric patients have not been established.

Unexpected AEs/ADRs will be classified by medical review with reference to the local product document. Events already included in the “Precautions for use” section of the local product document will be classified as “expected”. All other events that are not included in the “Precautions for use” section of the local product document will be classified as “unexpected”. An unexpected AE includes any events that may be symptomatically and patho-physiologically related to an event listed in the labeling, but differs from the labeled event because of greater severity or specificity.

In the case of an adverse event with important potential risks and important identified risks in relation to the safety specification under the risk management plan, or if missing information patient group is recruited, actions according to the label will be taken, and the safety information is presented separately.

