7.2.5.2. Demography and baseline characteristics

The following will be recorded on the CRF for each patient:

- Age: Record actual age of the patient at the time of enrollment. The age should be calculated by the date of birth.
- Sex: Check the box next to “male” or “female” on the CRF.
- Height: Record by unit of cm.
- Weight: Record by unit of kg.
- Herpes zoster vaccination: Record if the patient had received vaccine of herpes zoster: yes; no; unknown.
- Smoking: Record smoking status of the patient: ex-smoking; current smoking; non-smoking; unknown.
- Duration of the disease: Record the duration of disease since the date that the patient was initially diagnosed with UC.
- Severity of disease activity: Assess the severity (Mild, Moderate, Severe) by measuring Mayo or partial Mayo score and calculating the total score of 12 or 9 points based on clinical evaluation criteria: Stool frequency, rectal bleeding, findings of endoscopy, and physician's global assessment. Partial Mayo score excludes the findings of endoscopy. The severity for partial Mayo score is defined as 0-1 for remission, 2-4 for mild, 5-6 for moderate and 7-9 for severe disease activity.

- Previous UC treatments: Only record UC treatments received 6 months prior to the initiation of Xeljanz. Record name of the medication/therapy, route and duration of the administration, and overall response, if possible.
- Latent tuberculosis: Record if the patient has latent tuberculosis: yes; no; unknown.
- Renal impairment: Record if the patient has renal disorder: yes (severe/moderate/mild); none.
- Hepatic impairment: Record if the patient has hepatic disorder: yes (severe/moderate/mild); none.
- Other past/present diseases: Record “yes” or “no” for medical history. If “yes”, record adequate full name of the past or present disease according to the Medical Terminology Dictionary written by the Korean Medical Society. Past or present disease will be determined based on the date of the first dose of Xeljanz.

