7.2.5.4. Concomitant treatments

Any concomitant treatments should be recorded on the CRF for each patient. The information should include:

- Name of the drug: Record generic name of the concomitant medication.
- Daily dose: Record single dose and dosing frequency of the concomitant medication.
- Duration of the treatment: Record the start date and stop date (year/month/day) of the concomitant medication. If the medication is being continued at the completion of the study, record the start date only and check “ongoing”.
- Purpose of the treatment: Record purpose of the concomitant treatment in detail.

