7.3.1.1. Adverse events

Please refer to [Section 9](#) for the definition of non-serious and serious adverse events (SAEs).

Any AEs observed and reported within the reporting period will be recorded on the CRF by the investigator, regardless of the causal relationship with Xeljanz (see [Section 9.2](#)). The AEs can be reported by the patients. The investigator will also collect AE data by asking the patient questions such as “Have you had any health problem since the last visit?”

Check either “yes” or “no” in the AE section of CRF. If “yes”, record the following information:

Event name: Record the name of the AE according to the MedDRA(Medical Dictionary for Regulatory Activities). If there is no appropriate term in the MedDRA, record the name of the AE according to the Medical Terminology Dictionary written by the Korean Medical Society. If possible, specify diagnosis, not individual symptoms.

Date of onset: Record the onset date of the AE. Record approximate date if an actual date is unknown.

Date of recovery: Record the stop date of the AE if the outcome of the AE is recovered or recovered with sequelae (see below). Record approximate date if an actual date is unknown.

Seriousness: Check either “yes” or “no” to indicate if the event is a SAE. If “yes” record appropriate category of the seriousness (see [Section 9](#)for the definition and reporting of SAEs).

Severity: Evaluation of AE severity must be done according to the following categories:

- **Mild**: Not causing any significant problem to the patient. Administration of medicinal product continues without dose adjustment.
- **Moderate**: Causes a problem that does not interfere significantly with usual activities or the clinical status. Dose of the medicinal product is adjusted or other therapy is added due to the AE.

- Severe: Causes a problem that interferes significantly with usual activities or the clinical status. The medicinal product is stopped due to the AE.

If the severity of an AE changes, the AE must be entered separately. Record the stop date of the previous severity and onset date of the new severity – along with completion of all other related items.

Causality assessment: The causal relationship of AEs to the medicinal product must be allocated by the investigator according to the following criteria in alignment with the requirements of MFDS:

- Certain
 - It follows a reasonable time sequence from administration of the drug (before and after the study medication);

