7.7.4 Statistical consideration

For the safety and effectiveness outcome variables, the statistically significant differences for each classification group are statistically processed using the χ^2 test ($p \leq 0.05$). The incidence of each anomaly is presented with a 95% confidence interval. In order to analyze the factors affecting safety, a list of abnormal case expressions was prepared by the types of abnormal cases and by the background factors of the subjects (by gender, age and the presence or absence of accompanying diseases). Analyze the factors using a categorical data analysis method (Chi-square test, Fisher's Exact test). For statistically significant items, the pharmacological significances are described, and major adverse events, drug adverse reactions, and unexpected adverse events will be summarized in a table.

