### 6.1.4. Concomitant Medication

Concomitant medication will be analyzed as all treatment included present ulcerative colitis treatment and other concomitant medication except previous ulcerative colitis treatment.

- 1) Concomitant medication will be presented in frequency and percentage.
- 2) Concomitant medication classified by Level 1 and Level 2 according to the latest version of ATC classification system in detail will be summarized with the number of subjects having concomitant medication, percentage and the number of concomitant medication.

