## **Statistical Analysis Plan for rPMS**

- Occurrence status of adverse events by their seriousness [SAE]
  - Results in death
  - Is life-threatening
  - Requires inpatient hospitalization or prolongation of hospitalization
  - Results in persistent or significant disability/incapacity
  - Results in congenital anomaly/birth defect
  - Other important medical event
- [Non-SAE]
- Occurrence status of adverse events by action taken
  - Permanently discontinued
  - Temporary discontinued or delayed
  - Dose reduced
  - Dose increased
  - No change
  - Not applicable
- Occurrence status of adverse events by their causality assessment to Xeljanz®
  - Related to Xeljanz®: ① Certain  
② Probable/likely  
③ Possible  
⑤ Conditional/unclassified  
⑥ Unassessable/unclassifiable  
⑦ Not applicable
  - Not related to Xeljanz®: ④ Unlikely
- Occurrence status of adverse events by their other causality assessment (In case of 'Unlikely')
  - Disease under the study
  - Other diseases
  - Concomitant treatment-medication or non-medication
  - Other

3) Occurrence status of adverse events by demographic and other baseline characteristics

- The incidence of adverse events and 95% C.I will be presented by categorical variables of demographic and other baseline characteristics.
- To identify statistically significant difference in the incidence of adverse events by categorical variables of demographic and other baseline characteristics, Chi-square test ( $\chi^2$  test) or Fisher's exact test (if the expected frequency for each cell under 5 is more than 20%) will be performed.

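### AE incidence is compared by concomitant medication with no first-dose cut-off, so drugs started to treat an AE can make the factor look like a cause of AEs

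*Protocol*

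**What the plan says.** Protocol 7.7.1 states the aim: "To identify the factors that affect safety, subgroup analysis for various factors will be performed". The analyses it names include a "comparison of incidence of AEs by sex, age, presence of concurrent diseases, presence of concomitant medications, baseline disease activity, etc". Disease activity in that list is tied to baseline; concomitant medication has no time reference.

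The only definition of the variable for analysis is in SAP 6.1.4: "Concomitant medication will be analyzed as all treatment included present ulcerative colitis treatment and other concomitant medication except previous ulcerative colitis treatment". The one timing split for medication, in SAP 6.1.2, sets aside UC treatment that ended before Xeljanz. Nothing sets aside drugs started after the first dose.

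Protocol 7.3.1.1 expects AEs to lead to new treatment. Its description of a moderate AE reads: "Dose of the medicinal product is adjusted or other therapy is added due to the AE".

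For diseases, Protocol 7.2.5.2 does fix the reference date: "Past or present disease will be determined based on the date of the first dose of Xeljanz". Neither document has a matching sentence for medication.

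SAP 6.2 item 3 gives the purpose of the tests: "To identify statistically significant difference in the incidence of adverse events by categorical variables of demographic and other baseline characteristics". Item 4 adds a logistic regression on the same set of factors. Neither item lists the factors. On significant results, Protocol 7.7.4 says: "For statistically significant items, the pharmacological significances are described".

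**The concern.** A factor that is meant to explain AEs must be fixed before the AEs can occur. Under the written definition, the outcome can create the exposure. A patient who takes nothing else at first dose and is then prescribed a drug for an AE counts as having concomitant medication. An identical patient without an AE counts as having none. This moves AE patients from the unexposed to the exposed group and never the other way, so the error always makes concomitant medication look harmful.

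A factor that reaches significance is to be given a pharmacological interpretation under Protocol 7.7.4, and odds ratios from the logistic model go into the re-examination report. An artefact of coding could then be presented to the regulator as a risk factor.

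**Working it through.** The documents state no figure for this comparison, and SAP 2.4 says sample size calculations do not apply, so there is no plan figure to reproduce. The check asks what the planned test would show if concomitant medication had no effect at all on AEs.

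**Inputs from the documents**
- Two-sided 5% level (SAP 5.1).
- Chi-square test, or Fisher's exact test when more than 20% of expected counts are under 5 (SAP 6.2 item 3).
- N = 600 (SAP 2.4). Also N = 90, implied by Protocol section 5, where 18 long-term users are 20% of those enrolled: 18 / 0.20 = 90.

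**Inputs assumed, because the documents give none**
- b, the share on a concomitant drug at first dose: 50% to 95%.
- t, the share of AE patients given a new drug for the AE: 20% to 60%.
- s, the share starting a drug for unrelated reasons: 0, then 20%.
- AE incidence: 15%, 30% and 50%.

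**Odds ratio with no true association**

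Share classed as exposed among AE patients: c1 = 1 − (1 − b)(1 − t)(1 − s). Among AE-free patients: c0 = 1 − (1 − b)(1 − s).

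OR = [c1/(1 − c1)] / [c0/(1 − c0)]. It does not depend on the AE incidence.

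- Lowest: b = 0.95, t = 0.2, s = 0. c1 = 0.96, c0 = 0.95, OR = (0.96/0.04)/(0.95/0.05) = 24/19 = 1.26.
- Highest: b = 0.5, t = 0.6, s = 0. c1 = 0.80, c0 = 0.50, OR = 4/1 = 4.0.
- Example: b = 0.6, t = 0.5, s = 0. c1 = 0.80, c0 = 0.60, OR = 4/1.5 = 2.67. At 30% AE incidence, AEs occur in 0.24/0.66 = 36.4% of exposed patients and 0.06/0.34 = 17.6% of unexposed patients.

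**Dilution by unrelated starts (same example)**
- If 20% of all patients start an unrelated drug: c1 = 1 − 0.4 × 0.5 × 0.8 = 0.84, c0 = 1 − 0.4 × 0.8 = 0.68, OR = 5.25/2.125 = 2.47.
- If only AE-free patients do: c1 = 0.80, c0 = 0.68, OR = 4/2.125 = 1.88.

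**Chance of p ≤ 0.05 with no true effect**

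The SAP test was simulated with 4,000 studies per setting at 30% AE incidence. Ranges are over t = 20% to 60%. The filtered columns count only drugs in use at first dose.

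| Baseline use | N=600, as written | N=90, as written | N=600, filtered | N=90, filtered |
|---|---|---|---|---|
| 60% | 46–100% | 10–63% | 4.7% | 5.3% |
| 80% | 20–98% | about 5–23% | 5.6% | 4.1% |
| 95% | 8–38% | about 0.4–1.5% | 4.8% | 1.8% |

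Over the whole grid, with b from 50% and AE incidence from 15% to 50%, the range as written is 4% to 100% at N = 600 and from under 1% to 86% at N = 90.

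**Separate check at 40% AE incidence** (1,000 studies per setting)
- b = 70%, t = 30%: AE incidence 42.9% against 31.8%, OR 1.61, significant in 16% of studies at N = 90 and 72% at N = 600.
- t = 10%, b = 50% to 90%: OR 1.12 to 1.22, significant in 3% to 6% of studies at N = 90 and 8% to 24% at N = 600.

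**The case against.** The strongest reply is that the SAP may never run this test on this variable. Protocol 7.7 lets the SAP modify the analysis plan, and SAP 6.2 items 3 and 4 speak only of demographic and baseline factors. SAP 6.1.1 lists ten such items and concomitant medication is not among them. The opening sentence of SAP 6.1 names concomitant medication separately and describes a purely descriptive purpose. On this reading the factor is either dropped or used in a baseline form. The dummy tables that might settle it are not in the text available for review.

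That ambiguity is real, but it does not remove the problem. Protocol 7.7.1 names the comparison, and nothing in the SAP withdraws it. SAP 6.1 as a whole carries the demographic and baseline title and contains 6.1.4, so the definition without a cut-off is the one an analyst would find.

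Three further points stand in part.
- Protocol 7.7.4 gives sex, age and accompanying disease as its background factors, not medication. The step to a pharmacological interpretation is therefore less direct than for those factors.
- The first-dose rule for diseases may have been written only to separate past from present disease. It still has the effect that medication lacks.
- The size is uncertain. Present UC treatment counts as concomitant medication, so baseline use may be high. With about 90 patients, and either very high baseline use or few AE patients given a drug, a false flag is no more likely than the nominal 5%. The odds ratio is still biased upwards.

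**Conclusion.** The concern holds. Read as written, the comparison in Protocol 7.7.1 uses a factor that AEs themselves can switch on. The bias is towards harm whenever some AE patients are given a new drug and that effect is not offset by drugs started for other reasons in AE-free patients.

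Its size rests wholly on assumed inputs: a spurious odds ratio of 1.26 to 4.0 over the ranges used. The chance of a false flag runs from negligible (N = 90, nearly everyone already on another drug) to near certain (N = 600, moderate baseline use, most AE patients treated).

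The damage is confined to one secondary comparison and to any model that carries the same variable. The primary overall AE incidence and its 95% confidence interval do not depend on it. The change should be made, but the main result does not turn on it.

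**What to change.** In Protocol 7.7.1, and in SAP 6.2 items 3 and 4 wherever the factor is used, define it as concomitant medication in use at the first Xeljanz dose: started on or before that date and not stopped before it. List the factors in SAP 6.2 so that it is clear whether this one is included. SAP 6.3 items 6 and 7 draw on the same set of factors and should use the same definition; SAP 6.4 repeats these analyses and would inherit it. Keep SAP 6.1.4 as the descriptive definition. Show drugs started after the first dose in a separate table by start date relative to AE onset, without a test.

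The cost is about one sentence in each document and a date filter. No new data are needed: Protocol 7.2.5.4 already says "Record the start date and stop date (year/month/day) of the concomitant medication", and it also collects the purpose of each treatment.

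The downside is small. Drugs started after the first dose but before an AE leave the tested comparison and appear only descriptively. Counting drugs up to AE onset is not a clean alternative, because AE-free patients have longer in which to start one. With 60% baseline use, 20% unrelated starts and AE onset halfway through on average, c1 = 1 − 0.4 × 0.9 = 0.64 and c0 = 1 − 0.4 × 0.8 = 0.68. That gives a spurious OR of (0.64/0.36)/(0.68/0.32) = 0.84, a bias in the opposite direction.
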